Up to 27 subjects are planned to be entered in this trial. Cohort 1 was planned to have 6 subjects, but enrollment was stopped after 5 subjects when brequinar PK and DHO results became available. These results led to study design changes as described here. The sixth subject will not be enrolled in Cohort 1.

Cohort 2 will enroll approximately 6 subjects, followed by an expansion cohort of approximately 15 subjects. All subjects in Cohort 2 will start with a 500 mg/m² dose once-weekly. Brequinar PK and DHO samples will be obtained for these subjects in Week 1 and results used to make decisions about the Week 2 once-weekly dose. Brequinar PK and DHO samples will also be obtained for Week 2 and the results used to make decisions about Week 3 dose frequency (once or twice-weekly) and the dose. The dose will be adjusted for each subject to meet the twice-weekly brequinar PK and 72-hour DHO criteria, and the Week 2 procedures may be repeated if needed until the twice-weekly dose is found.

After both the brequinar PK and 72-hour DHO level meet criteria described in the Individual Dose Adjustment Guidelines as described in Protocol Section 8.5, a subject may move to twice-weekly dosing on a continuing basis as tolerated. The twice-weekly dose may be further adjusted using 84-hour DHO (trough ~ 84 hours after dosing) criteria, also described in the Guidelines for Individual Dose Adjustment.

Dosing will continue up to 12 months in the absence of unacceptable toxicity or disease progression, or may be discontinued with Sponsor consent after completing at least 6 weeks of dosing.

B. Study Population

Up to 27 subjects 18 years or older with relapsed/refractory AML by World Health Organization (WHO) classification who have exhausted available therapy and who meet all inclusion/exclusion criteria will be enrolled at 3- 6 sites in the United States.

C. Sample Size Predictions

Formal sample size calculations are not applicable to this phase 1b/2a dose-adjustment and expansion study.

V. General Analytical Considerations

All analyses of safety and anti-leukemic activity for this open-label, early-phase study will be descriptive in nature and presented by dose group and overall, as appropriate, for dose-adjustment and expansion phases.

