Statistical code and outputs for analyses will be generated using SAS/STAT and SAS/GRAFH software, version 9.3 or higher, of the SAS system for Windows. Copyright © [2011] SAS Institute Inc. SAS and all other SAS Institute Inc. product or service names are registered trademarks or trademarks of SAS Institute Inc., Cary, NC, USA.

A. Data Sources

The study center staff will record completion and results of required study procedures in an electronic case report form (eCRF). The following external data obtained from third-party vendors for this study will be combined with eCRF data for analysis:

Vendor Name	Contact Information	Data Type	Schedule	Reconciliation Items
Pyxant	TBD	DHO plasma levels and brequinar PK results	2 transfers during study	Header data (subject ID, initials, visit, lab date, lab time)

B. Multiple Study Centers

Data analyses will be pooled and not controlled for center effect.

C. Definition of Baseline

Baseline will be defined as the last measurement collected before the first dose of study drug. As such, height and body surface area assessed at Screening, and pre-dose assessments made on Cycle 1 Week 1 Day 1 for weight, vital signs, hematology/chemistry, and 12-lead ECG will serve as valid baseline measures. A missing value at Cycle 1 Week 1 Day 1 will default to the Screening measurement.

For this study, since there is no day 0, the day immediately prior to study day 1 will be Day -1 [calculated as Event Date – Date of First Treatment]. For events on or after first dose of study drug, study day will be calculated as [Event Date – Date of First Treatment + 1]. Thus, first day of study drug dose will be Day 1.

D. Missing Data

Unless stated otherwise in sections below, missing data will not be replaced with imputed values.

E. Analysis Populations

Four analysis population sets will be defined for use with various analyses, namely:

- The Enrolled Analysis Set will include all subjects who sign informed consent, meet the inclusion/exclusion criteria and are enrolled in the study. Demographics and disposition summaries will be reported for this set of subjects.
- The Safety Analysis Set will include all subjects who are enrolled in the study and receive at least one dose of brequinar. Subjects in this set will be used for all safety/tolerability summary tables.

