- AML supplemental tests: Cytogenetics and molecular data information recorded on the eCRF will be listed, including information on karyotypic, Fluorescence in situ hybridization (FISH), and gene fusion analysis, as well as all present mutations.
- Prior cancer drug treatment: A listing will display all entries for prior cancer medications received by a subject, ordered by “Start date”. A summary table will summarize the following characteristics:
 - Number of subjects reporting at least one prior cancer drug treatment.
 - Drug treatment type (Chemotherapy, Targeted therapy, Immunological, Not Applicable).
 - Drug treatment combined with radiotherapy (No/Yes).
 - Number of cycles received.
 - Best response under treatment (Complete remission, Complete remission with incomplete hematologic recovery, Complete remission with partial hematologic recovery, Morphologic

leukemia-free state, Partial remission, Stable disease, Progressive disease, Unknown).

- Relapse (derived as ‘Yes’ if date of relapse is not blank. ‘No’ otherwise).
- Prior cancer non-drug treatment: All non-drug treatments received will be listed in order of “Start date”. Summary statistics will be provided for:
 - Number of subjects reporting at least one prior cancer non-drug treatment.
 - Treatment type (Radiation, Surgery, Other).
 - Intention (Palliative, Therapeutic).
 - Best response under treatment (Complete remission, Complete remission with incomplete hematologic recovery, Complete remission with partial hematologic recovery, Morphologic leukemia-free state, Partial remission, Stable disease, Progressive disease, Not applicable, Unknown).
 - Relapse (derived as ‘Yes’ if date of relapse is not blank. ‘No’ otherwise).

D. Protocol Deviations

A listing will be provided for all protocol deviations.

VII. Safety Analyses

To meet the primary objective of the study, all safety analyses will be performed on the Safety Analysis Set of subjects.

A. Exposure

For each subject, the assigned dose level of brequinar (mg/m^2), the assigned dose (mg), dose day, date and time taken, whether entire dose was taken, number of capsules taken, total dose taken (mg), and the reason for missed dose (partial or complete) will be listed by treatment group and visit cycle.

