Summary statistics will be presented for assigned dose level, cumulative assigned dose, cumulative actual exposure (mg), total duration of treatment (calculated as the number of weeks from date of first drug dose to date of last drug dose), dose intensity (calculated as cumulative actual exposure divided by treatment duration, mg/week), relative dose intensity (calculated as a percent of cumulative actual drug dose divided by cumulative assigned dose), and any reason for missed dose.

B. DHO Plasma Levels

In addition to safety/tolerability, intra-subject dosing for this study will be guided by DHO levels measured using a validated assay. A subject listing will include baseline and trough DHO levels (ng/ml), as well as the following additional characteristics noted at each scheduled visit:

- Previous assigned dose (mg/m²).
- DHO dose adjustment (dose not changed, escalated by 150 mg/m², held, Cohort 1 dose escalation not permitted).
- Assigned dose based on DHO (mg/m²).
- PI evaluation of whether subject has acceptable safety, safety dose adjustment, and assigned dose.
- Actual dose (mg).
- Agreement between PI assessment and actual dose (No/Yes, reason for disagreement).

The above dose-modification characteristics will also be summarized by treatment group and overall.

C. Dose Limiting Toxicities

AEs identified as protocol-defined DLTs will be listed and will include start and end dates, CTCAE grade, relationship to study drug, outcome, and action taken. Number and percentage of subjects reporting DLTs in each treatment group, and overall, will be summarized.

D. Adverse Events

AEs will be collected from time of informed consent through at least 14 days after the final dose of study medication. Any pre-existing condition that changes in severity after dosing or abnormal laboratory finding will be recorded as an AE. Events that occur prior to dosing will be recorded as medical history. A TEAE for this study will be defined as an AE occurring after the first dose of the study treatment through 30 days after the last dose of study treatment.

Verbatim terms on the eCRF will be coded using the MedDRA version 21.1 and displayed hierarchically by system organ class and preferred term. Multiple incidences of the same AE for a subject will be counted only once at the maximum CTCAE grade.

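### SAP Section VII.A: dose intensity omits the interval after the last dose, so mg/week is doubled after two weekly doses, 20% too high after six, and undefined after one

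*SAP*

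**What the plan says.** Section VII.A of the SAP fixes both parts of the calculation. Among the measures to be summarised it lists "total duration of treatment (calculated as the number of weeks from date of first drug dose to date of last drug dose), dose intensity", and it defines the rate as "dose intensity (calculated as cumulative actual exposure divided by treatment duration, mg/week"). The same sentence defines "relative dose intensity (calculated as a percent of cumulative actual drug dose divided by cumulative assigned dose"), which has no time component.

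Dosing is intermittent. Under Section IV.A (Design Overview), Cohort 2 starts once-weekly. Week 2 samples are then taken, with "the results used to make decisions about Week 3 dose frequency (once or twice-weekly) and the dose". Once a subject is dosed twice-weekly, "The twice-weekly dose may be further adjusted using 84-hour DHO (trough ~ 84 hours after dosing) criteria", which puts the twice-weekly interval at about 84 hours.

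Single-dose subjects are included. The Safety Analysis Set in Section V.E takes all enrolled subjects who "receive at least one dose of brequinar. Subjects in this set will be used for all safety/tolerability summary tables", and Section VII confirms that "all safety analyses will be performed on the Safety Analysis Set of subjects".

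**The concern.** A rate per week should credit each dose with the time it covers. Here every dose is in the numerator, but the last dose contributes no time to the denominator. With daily dosing the loss would be one day. In this trial it is 7 days, or about 3.5.

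The bias depends on how long a subject is treated. It is largest for those who stop early, so at the same dose and schedule a group with more early stopping would look more intensively dosed. It also blurs the once-weekly versus twice-weekly distinction: a once-weekly subject who stops after two doses of D mg is reported at 2D mg/week, the true rate of a twice-weekly subject on the same dose. Subjects with a single dose have a zero denominator, and Section VII.A gives no rule for them.

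**Working it through.** The SAP gives no dose-intensity figure to reproduce, so the check applies its definition to simple dosing histories.

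**Inputs**
- Duration and dose-intensity formulas: SAP Section VII.A.
- Interval g: 7 days once-weekly; 84/24 = 3.5 days twice-weekly (Section IV.A).
- Reference points: six weeks as the earliest stop with sponsor consent, and 12 months as the maximum (Section IV.A).
- Assumed: n equal doses of D mg, none missed.

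**Even spacing**
- SAP rate = nD / [(n − 1)g/7].
- Delivered rate = 7D/g.
- Ratio = n/(n − 1), for any g and D.

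| Doses n | SAP ratio | Ratio if one day is added, once-weekly: 7n/(7(n − 1) + 1) |
|---|---|---|
| 1 | undefined (D/0) | 7.00 |
| 2 | 2.00 | 1.75 |
| 3 | 1.50 | 1.40 |
| 4 | 1.33 | 1.27 |
| 6 | 1.20 | 1.17 |
| 12 | 1.09 | 1.08 |
| 26 | 1.04 | 1.03 |
| 52 | 1.02 | 1.02 |

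The last column tests a natural repair. Section V.C adds one day when computing study day, but the SAP does not apply this to duration. It would remove the zero denominator and leave most of the bias.

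**Weekly in Weeks 1–2, twice-weekly from Week 3**

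Doses within a week are taken as 3 or 4 days apart. The comparison is with a denominator that adds 3.5 days, so ratio = (span + 3.5)/span.
- End of Week 3: 4 doses, span 17 or 18 days; 20.5/17 = 1.21 or 21.5/18 = 1.19.
- End of Week 4: 6 doses, span 24 or 25 days; 27.5/24 = 1.15 or 28.5/25 = 1.14.
- End of Week 6: 10 doses, span 38 or 39 days; 41.5/38 = 1.09 or 42.5/39 = 1.09.
- End of Week 12: 22 doses, span 80 or 81 days; 83.5/80 = 1.04 or 84.5/81 = 1.04.

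**In mg/week**

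The SAP gives no body surface area, so 1.8 m² is assumed, with a range of 1.5 to 2.2. At the 500 mg/m² start, one weekly dose is 500 × 1.8 = 900 mg (750 to 1100).
- After 2 weekly doses: 2 × 900/1 = 1800 mg/week reported (1500 to 2200), against 900 delivered.
- After 6 weekly doses: 6 × 900/5 = 1080 mg/week reported (900 to 1320), against 900 delivered.

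**With the last interval added**

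Rate = nD/(ng/7) = 7D/g. The ratio is 1.00 for every n, including n = 1.

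**The case against.** The strongest case on the other side is that little depends on this number. All safety and activity analyses are descriptive, and no planned analysis links dose intensity to outcome. Cumulative exposure and relative dose intensity are unaffected, and the exposure listing shows every dose with its date and milligrams, so a reader could recompute the rate for each of at most 27 subjects. That stands, and it limits the priority. It does not make the defined quantity correct, and this is the only exposure summary expressed per week.

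The single-dose case is partly covered. Section V.D does not impute missing data, and Section V.F reports the number of nonmissing values, so a non-computable value would probably be shown as missing with a smaller n. Neither section mentions a zero denominator, and the overstatement for everyone else remains.

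The larger percentages belong to once-weekly dosing, whereas the design aims to move subjects to twice-weekly from Week 3, where the excess is smaller. That is fair. Weekly dosing can nevertheless last longer, because Section IV.A lets the Week 2 steps be repeated.

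Finally, the 3.5-day interval is itself a convention. With doses 3 or 4 days apart it gives 20.5 or 21.5 days where three full weeks are 21, an error of about 2%. This is small beside the roughly 20% it removes at that point.

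**Conclusion.** The concern holds. Followed as written, Section VII.A overstates the delivered mg/week by a factor of n/(n − 1) for evenly spaced doses and gives no value for a single dose. For once-weekly dosing the excess is 100% after 2 doses, 50% after 3, 20% after 6, and 2% to 4% for 52 and 26 doses. On the path to twice-weekly dosing from Week 3 it is 19% to 21% at three weeks, about 9% at six and 4% at twelve.

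These sizes assume equal doses with none missed. The mixed-schedule figures also assume the 3.5-day convention. The SAP gives no treatment durations, so the effect on a group mean or median cannot be known in advance; it depends on how many subjects stop early. No error rate, endpoint or efficacy conclusion is affected. The definition should be corrected because it is simply wrong for the rate it names.

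**What to change.** Keep total duration of treatment as first to last dose if that is wanted, and define a separate denominator for dose intensity, applied to every Safety Analysis Set subject including those with one dose:

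weeks = (date of last dose − date of first dose + scheduled dosing interval in force at the last dose) / 7

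The interval is 7 days if the subject was on once-weekly dosing at the last dose and 3.5 days if on twice-weekly. The SAP should also say how that frequency is derived. The Section VII.A listing names no frequency field, although it may be derivable from the dose days and dates.

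The cost is one added derivation in the SAP and its code, plus the frequency rule. One small drawback should be stated with the definition: a full interval is credited by convention even when a subject stops or dies soon after the last dose.

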Extra measurements (such as unscheduled or repeat assessments) will be included in subject listings but not in summary tables.

Figures will be produced as specified in sections to follow.

VI. Subject Accountability

A. Analysis Populations

A summary table will present counts and percent of subjects in the study analysis populations of Enrolled, Safety, Efficacy, and PK Analysis sets by treatment group.

B. Disposition

All subjects who discontinue treatment or withdraw early from the study will be included in a listing. Disposition summaries will present number of subjects enrolled, number treated, and among those treated number who completed and discontinued treatment. Primary reason for discontinuation of treatment, including any of the following, will be summarized:

- Adverse event
- Physician/Sponsor decision
- Pregnancy
- Protocol defined disease progression
- Study terminated by sponsor
- Subject non-compliance/Protocol violation(s)
- Withdrawal of consent.

Counts and percentages of subjects who withdraw early from the study for any of the above reasons will also be calculated using all members of the relevant population in the relevant treatment group for the denominator.

C. Subject Characteristics

The following subject characteristics collected for the Enrolled Analysis Set will be presented in data listings and summarized by treatment regimen and overall:

Demography:

- Age: Age will be calculated as the number of years elapsed between birth date and the date of the screening visit, adjusted for whether the birthday has passed as of the day of the screening visit.
- Sex at birth
- Ethnicity
- Race

Medical History:

- Medical history: As noted on the Medical History eCRF, any significant medical conditions present prior to signing consent will be presented in a listing and summary table. Verbatim terms will be coded using the MedDRA version 21.1 and ordered by system organ class (SOC) and preferred term (PT). At each level of summation (SOC, PT), subjects reporting more than one medical condition will be counted only once.
- AML disease information: Disease characteristics of initial diagnosis of AML recorded on the eCRF, along with time since initial diagnosis (calculated as date of informed consent – date of initial diagnosis of AML/365.25), will be listed and summarized.

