A summary table will be constructed to display the anatomical main class (1st level) of each coded medication and, within that, the pharmacological subgroup (3rd level). It will include counts and percentages of subjects who reported using at least one medication in each pharmacological subgroup.

L. Blood Transfusions

Any blood transfusions received up to eight weeks prior to Cycle 1 Day 1 (baseline event), and during the study, including start and end dates, blood product, total number of units received, and reason for transfusion will be listed and summarized.

VIII. Efficacy Analyses

The secondary objectives of the study will be addressed using the Efficacy Analysis Set of subjects.

A. Disease Response

As per criteria defined in the ELN Guidelines by [Dohner et al, 2017](#), disease response will be assessed at screening and post-screening visits and included in a data listing. Additionally, anti-leukemic activity will be evaluated as per the following outcomes:

Response Rates: The distribution of best overall response (BOR) of CR, CRi, CRh, MLFS, or PR will be summarized by treatment cohort and overall. Point estimates with two-sided exact 95% and 90% confidence intervals (CIs) will be included for:

- Overall response rate (ORR) defined as the proportion of subjects who achieve a best overall response of CR, CRi, CRh, MLFS, or PR.
- Complete remission rate defined as the proportion of subjects who achieve a best overall response of CR.
- Complete remission with incomplete hematologic recovery rate defined as the proportion of subjects who achieve a best overall response of CRi.
- Complete remission with partial hematological recovery rate defined as the proportion subjects who achieve a best overall response of CRh.
- Morphological leukemia-free state rate defined as the proportion of subjects who achieve a best overall response of MLFS.
- Partial remission rate defined as the proportion of subjects who achieve best overall response of PR.

Additional information on precise definitions of these response categories can be found in Section 10.3 of the protocol.

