Duration of Response: Duration of response will be defined as the time from the first occurrence of a qualifying response of CR, CRi, CRh, MLFS, or PR, to the date when progressive disease is objectively documented or death due to any cause, whichever occurs earlier. Following the qualifying response, subjects who are alive without disease progression will be right-censored at the date of last disease evaluation. A Kaplan-Meier graph will be plotted by treatment group and estimates of median duration with associated 95% CIs will be reported.

Event-free Survival (EFS): Event-free survival will be determined from the first dose of brequinar to the date of relapse ($\geq 5\%$ bone marrow blasts, reappearance of blasts in blood, or development of extramedullary disease), disease progression, or death, whichever occurs first. Subjects who do not experience any of the three events will be right-censored at the latter date of disease evaluation or bone marrow sampling. A Kaplan-Meier graph will be plotted for time to the composite outcome by treatment group, and the estimate of medial survival time with 95% CI will be summarized.

Overall Survival (OS): Overall survival will be calculated as the time from the first dose of study drug to the date of death or right-censoring at the date of last subject contact. Median time to OS, with 95% CI, will be summarized and displayed graphically by treatment group using the Kaplan-Meier method.

B. Clinical Benefit

In addition to ORR, this study will examine clinical benefit to subjects. By treatment group, a summary table will report counts and percent of transfusion-dependent subjects at baseline who, in the absence of progression, CR or PR, and independent of marrow response, achieve one of the following:

- Erythroid response: Transfusion Independence (TI) for 8 or more weeks for subjects requiring at least 4 units of packed red blood cell transfusions in the previous 8 weeks. Only red blood cell transfusions given based on physician's judgment for a pretreatment hemoglobin (Hgb) of ≤ 8.5 g/dL will count in the red blood cell TI response evaluation.
- Platelet response: TI for subjects requiring a minimum of 4 platelet transfusions in the previous 8 weeks.

IX. Pharmacokinetic Analyses

The plasma PK of brequinar and DHO will be characterized using non-compartmental analysis. Where possible, the following standard PK parameters will be calculated:

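### Duration of response stops only at progressive disease or death, while EFS in the same section counts relapse as a separate event; read literally, a relapse does not end a response and DOR is overstated

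*SAP*

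**What the plan says.** The relevant text is in SAP Section VIII.A, in two adjacent paragraphs.

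- **DOR, start:** "the time from the first occurrence of a qualifying response of CR, CRi, CRh, MLFS, or PR".
- **DOR, end:** "to the date when progressive disease is objectively documented or death due to any cause, whichever occurs earlier".
- **DOR, censoring:** "subjects who are alive without disease progression will be right-censored at the date of last disease evaluation".
- **EFS, end:** relapse, defined by marrow blasts of at least 5%, blasts returning in blood, "or development of extramedullary disease), disease progression, or death, whichever occurs first".
- **EFS, censoring:** "Subjects who do not experience any of the three events will be right-censored".

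Two other places touch on the meaning of progression. Under Disease Response in VIII.A, the SAP says "Additional information on precise definitions of these response categories can be found in Section 10.3 of the protocol"; the categories listed there are CR, CRi, CRh, MLFS and PR. Section VI.B lists "Protocol defined disease progression" as a reason for discontinuing treatment and gives no definition.

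DOR is a secondary objective (II.B) and is reported as a Kaplan-Meier median with a 95% CI.

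**The concern.** Relapse appears in neither the end rule nor the censoring rule for DOR. Yet four of the five qualifying responses (CR, CRi, CRh, MLFS) are those for which a relapse can be defined, and the EFS paragraph defines it. The count of three EFS events works only if relapse and progression are separate items.

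A programmer who follows that separation will derive DOR from progression and death alone. Another may treat relapse as progression. Both could claim to follow the SAP, and their DOR results would differ on the same data. Under the first derivation, one subject can have an EFS event on a date when DOR still counts the response as ongoing.

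**Working it through.** **1. The rules side by side**

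| What happens to a CR, CRi, CRh or MLFS responder | EFS | DOR as written |
|---|---|---|
| Relapse, later documented progression or death | Event at relapse | Event at the later date |
| Relapse, then neither | Event at relapse | Censored at last disease evaluation |
| Death without relapse | Event at death | Event at death |
| No event | Censored | Censored |

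Relapse is found at a disease evaluation, so a relapsed subject's DOR under the written rule is never shorter than the time to relapse. It is either a later event or a censored time.

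**2. Size with full follow-up**

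The SAP states no expected DOR, so there is no figure of its own to reproduce. All inputs here are assumptions. Times are exponential, with median m₁ from response to relapse and m₂ from relapse to death. A share p of relapses is recorded as progression on the relapse date. With a = ln 2/m₁ and b = ln 2/m₂, the DOR curve under the written rule is

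S(t) = p·e^(−at) + (1 − p)·[b·e^(−at) − a·e^(−bt)]/(b − a),

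where the bracketed term over (b − a) becomes (1 + at)·e^(−at) when a = b. The median solves S(t) = 0.5.

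For m₁ = 4 and m₂ = 3, a = 0.1733 and b = 0.2310.

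- p = 0, t = 8.44: e^(−at) = 0.2316 and e^(−bt) = 0.1423, so S = (0.2310 × 0.2316 − 0.1733 × 0.1423)/0.0577 = 0.500.
- p = 0.5, t = 6.13: S = 0.5 × 0.3457 + 0.5 × 0.6549 = 0.500.
- p = 1: the median is m₁ = 4.0.

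| m₁, m₂ (months) | p = 0 | p = 0.5 | p = 1 (correct) |
|---|---|---|---|
| 3, 2 | 6.0 | 4.5 | 3.0 |
| 4, 3 | 8.4 | 6.1 | 4.0 |
| 6, 6 | 14.5 | 9.9 | 6.0 |

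Nearer the null, for m₁ = 4 and m₂ = 3, p = 0.75 gives 5.0 months and p = 0.9 gives 4.4.

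**3. Size in a small sample**

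This is a simulation of 8,000 trials per setting. Assumptions: m₁ = 4, m₂ = 3, median 24 months to death without relapse, censoring uniform between 3 and 12 months, and every death before censoring counted. The typical value is the median of the Kaplan-Meier medians across trials.

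| Responders, p | Written rule (months) | Relapse counted (months) | Median not reached, written v counted |
|---|---|---|---|
| 8, p = 0 | 6.8 | 2.9 | 22% v 2% |
| 8, p = 0.5 | 4.5 | 2.9 | 9% v 2% |
| 8, p = 1 | identical | identical | identical |
| 4, p = 0 | 5.9 | 2.4 | 25% v 5% |
| 12, p = 0 | 7.1 | 3.1 | 18% v 1% |

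The 2.9 lies below 4.0 because a Kaplan-Meier median in 8 subjects falls at about the fourth event and deaths without relapse are events too.

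**4. Censoring at the last disease evaluation**

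A separate calculation applied the SAP's censoring point and counted later events only up to that evaluation. It assumed a median of 3 months to relapse, 12 months of follow-up, a median of 1, 2 or 4 months from relapse to later progression or death, and a last evaluation 0, 1 or 3 months after relapse. With relapse counted, the median is about 3.0 months. Under the written rule it is 4.7 to 11.7 months in five of the nine combinations and not reached in the other four.

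The upward shift is general but not certain at every time point in a very small sample. With 8 responders, the written-rule curve fell below the relapse-counted curve at 2,818 of 180,000 points checked (1.6%).

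**The case against.** The strongest reply is that progression is the SAP's umbrella term for loss of disease control. Dosing continues in the absence of toxicity or progression (IV.A), the discontinuation reasons name protocol-defined progression but not relapse (VI.B), and the clinical-benefit rule refers only to progression (VIII.B). If relapse were never progression, a relapsed responder would have no disease-based reason for stopping. EFS also covers non-responders, who can progress but cannot relapse, so naming both in a first-of composite may be harmless overlap. The protocol, which is not at hand, may settle the definition.

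This is a fair inference, and it is why the bias is stated as conditional. It is not a statement in the SAP, however. The pointer to protocol Section 10.3 covers the response categories, not progression. If progression does include relapse, the EFS wording of three events conflicts with that usage, so the adjacent paragraphs need reconciling either way. The prior-treatment items in VI.C list "Partial remission, Stable disease, Progressive disease, Not applicable, Unknown" among best responses and record relapse separately, but they concern earlier therapy and support the point only weakly.

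Three criticisms of the numbers stand. The largest figures assume that no relapse is recorded as progression; with 90% recorded, the 8-responder simulation gives about 3.1 v 2.9 months. PR responders are not modelled separately and would dilute the effect. The simulation in step 3 censors at an administrative date and not at the last disease evaluation, which step 4 addresses.

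**Conclusion.** The concern holds. As written, the DOR rule omits the event by which a CR, CRi, CRh or MLFS responder would lose response under the SAP's own EFS criteria, and it conflicts with the neighbouring paragraph. The overstatement depends on the literal reading and on how many relapses are recorded as progression. On the assumed medians of 4 and 3 months it runs from none (4.0 months, all recorded) to about double (8.4 months, none recorded). In small samples the written rule also makes an unreached median more frequent.

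The text conflict is certain; the size is illustrative. All analyses are descriptive, up to 27 subjects are planned, and EFS, which does count relapse, is reported alongside. The consequence is therefore a misleading secondary estimate, not a wrong test or dose decision. It should be fixed before the DOR programs are written.

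**What to change.** Define the end of DOR as the earliest of:

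- relapse by the EFS criteria, only for subjects whose response is CR, CRi, CRh or MLFS;
- objectively documented progressive disease, for all responders including PR;
- death from any cause.

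Censor only responders who are alive without relapse or progression, at the last disease evaluation. The marrow-blast criterion of at least 5% should not be applied to PR responders, who might meet it at the moment of response.

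The alternative is to state in the SAP that progressive disease includes relapse, and to reword EFS so that the two are no longer presented as separate events. Whichever is chosen should be checked against the protocol's definition of progression.

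The cost is one or two sentences. No new data are needed, because EFS already requires relapse dates. Reported DOR will be shorter than under the literal rule.
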